3.2. Specification for Measuring Methods

3.2.1. Measurement of Lesions

For clinical evaluation, the lesions are measured by a caliper (vernier caliper), and all measurements are recorded in metric unit. All baseline evaluations must be carried out as close to initiation of treatment as possible, and cannot be as early as 4 weeks.

3.2.2. Measuring Methods

Each reported lesion shall be described by the same judgment method and technique during the baseline and follow-up periods. Generally they are evaluated by imaging measurements other than clinical examination, unless it is found that the lesions are not suitable for imaging measurements during follow-up.

Clinical lesion: Only superficial lesions (such as small subcutaneous nodes) with a diameter of more than 10 mm, as measured by vernier caliper, are considered measurable. For patients with skin lesions, record by color photographs is suggested, in which the proportion for measuring lesion size is annexed. As previously mentioned, when the lesions may be examined clinically or by imaging technique, then it is examined by imaging technique, as imaging evaluation is more objective and may be used for final review of clinical investigation.

Chest X-ray radiography: Between chest CT and chest X-ray radiography, chest CT is selected preferentially, especially when progression of disease is used as an important endpoint variable, as CT scanning is more sensitive in identifying new lesions than X-ray radiography. However, if X-ray radiography visualizes clear border of lesions, surrounded by inflated lung, the lesions are considered measurable. See Appendix II for details.

CT and MRI: Presently, CT is the most efficient and of good repeatability test method used to evaluate lesions. As defined in the Guideline, measurable lesions are based on a layer thickness of not more than 5 mm, if CT scanning is used. As shown in Appendix II, when the CT layer thickness is more than 5 mm, the minimum measurable lesion is 2 times the layer thickness. MRI may also be used in some cases (such as whole body scanning). See Appendix II for more comments on response evaluation in solid tumors by CT and MRI examinations.

Ultrasonography: Ultrasonography is not suitable to evaluate lesion size, and should not be used for measuring methods. Ultrasonography cannot be reproduced completely between two adjacent observations; moreover, the results are dependent on the examiner. Therefore same technique and same measurement results cannot be assured from one to another examination (see Appendix II for details). If new lesions are found by ultrasonography during research, it is suggested to confirm by CT or MRI. Upon worrying irradiation by CT, MRI may be used instead to examine the lesions.

Endoscopy and laparoscopy: it is not suggested that those techniques are used for response evaluation of tumors. However, they are useful in confirming complete pathological response by biopsy or in determining complete response or relapse after surgical resection.

Tumor marker: Tumor markers cannot be used alone to evaluate objective response of tumors. However, when tumor markers are higher than the normal upper limit, they must be standardized if they are used to judge complete response of a patient. As tumor markers are disease-specific, the description for the measurement technique should mark the records of baseline measurement for a special disease. The special guidelines on CA-125 changes (in relapse of ovarian carcinoma) and PSA change (in relapse of prostatic carcinoma) have been published. Moreover, the International Group (Intergroup) of Gynecological Oncology has formulated the criteria for CA125 progression, of which all will be used as firstline criteria for objective evaluation of tumors during trials in ovarian carcinoma.

Cytology and histology: If required by the clinical study protocol, those techniques may be used to distinguish partial response and complete response in individual patients (for example, residual benign tumor lesion in the tumor type of germ cell tumor). When it is known that exudate is a potential serious adverse consequence during treatment (such as some paclitaxel chemotherapeutic drugs or angiogenesis inhibitors), to distinguish effectiveness (such as stable disease) and progression of disease, attention must be paid to development or exacerbation of any new exudate, as proved cytologically during treatment, even though measurable tumors meet the criteria for effectiveness or stable disease.

4. Response Evaluation in Tumors

4.1 Evaluation of All Tumors and Measurable Lesions

To evaluate objective response or incoming potential progression, it is necessary to carry out a baseline evaluation for total tumor burden of all tumor lesions, for reference to subsequent measurements. In clinical protocol with objective response as primary treatment endpoint, only the patients with measurable lesions at baseline may be enrolled. Measurable lesions are defined as presence of at least one measurable lesion. For trials with progression of disease (time to progression of disease or progression degree on fixed date) as primary treatment endpoint, it must be clearly defined in the inclusion criteria in the protocol that it is restricted to only patients with measurable lesions or those with immeasurable lesions may be enrolled.

4.2 Baseline Records of Target and Nontarget Lesions

If there is more than 1 measurable lesions at baseline evaluation, all lesions are recorded and measured; not more than 5 lesions in total (not more than 2 lesions per organ) are used as target lesions, representing all involved organs (that is to say, for a patient with only 1 or 2 involved organs, 2 or 4 target lesions at maximum may be selected as lesions for baseline measurements).

Target lesions must be selected on the basis of their size (maximum diameter), and can represent all involved organs; moreover, measurement must be of good repeatability. Sometimes when the maximum lesion cannot be measured repeatedly, a second maximum lesion may be selected for repeated measurement.

As lymph nodes are normal tissues, they may be visualized even without any tumor metastasis, therefore they must be concerned particularly. Pathological lymph nodes defined as measurable nodes or even being target lesions must comply with the following criteria: The short diameter measured by CT is ≥ 15 mm. At baseline, only short diameter may be measured. A radiologist usually judges whether a node is with metastasis by the short diameter of the node. The size of a node is generally expressed by the 2-dimensional data of imaging examination (by axial plane in CT, or by one of axial plane, sagittal plane, or coronal plane in MRI). The minimum value is used as short diameter. For example, one abdominal node at 20 mm x 30 mm with a diameter of 20 mm may be considered as a malignant, measurable node. In this example, 20 mm is the measurement of the node. Nodes in a diameter of ≥ 10 mm but < 15 mm should not be considered as target lesion. Nodes in a diameter of < 10 mm do not belong to the category of pathological nodes, and are not recorded or subject to further observation.

The sum (containing the maximum diameter of nonnodular lesions, and short diameter of nodular lesions) of the diameters of all target lesions will be used as sum of baseline diameter of lesions and reported. If the diameter of a lymph node is included, as mentioned above, only short diameter are counted in the sum. The sum of baseline diameter will be used as reference value for the baseline level of disease.

Other all lesions including pathological lymph nodes may be considered as nontarget lesions, and need not be measured; however, they should be recorded at baseline evaluation. For example, they are recorded as "present", "absent", or "clearly progressed" in extremely rare cases. Extensively present target lesions may be recorded together with target organs (such as massively proliferated pelvic lymph nodes or large-scale metastasis to liver).

4.3. Criteria for Response Evaluation

In this section, the criteria for measuring objective response rate of target lesions of tumors are defined.

4.3.1. Response Evaluation of Target Lesions

Complete response (CR): All target lesions disappear, and the short axis value of any pathological lymph nodes (whether they are target lesions or not) must be <10 mm.

Partial response (PR): Using the overall diameter at baseline as reference, the sum of the diameter of all lesions is reduced by at least 30%.

Progression of disease (PD): Using the sum of the diameter of minimum lesions (including the sum of the diameter of lesions at baseline, if it is minimum), the sum of the diameter of all target lesions are increased by 20%. Moreover, in addition to the sum of the diameter is increased relatively by 20%, the absolute value of the sum must be increased by at least 5 mm (Note: one or more new lesions occurred may also be considered as progression of disease).

Stable disease (SD): Using the minimum sum of the diameter of the lesions during the study as reference, the lesion reduction does not meet PR, and lesion increase does not meet PD.

4.3.2. Precautions for Response Evaluation of Target Lesions

When the target lesions are lymph nodes:

Generally the measurement of its actual short axis (in the same anatomic plane as baseline) is recorded, even though all lymph nodes are subsided to a size of less than 10 mm. This means when the target lesions are lymph nodes, even meeting the criteria for complete response, the sum of the diameter of target lesions is not 0, as the lymph nodes in a short axis value <10 mm are defined as normal lymph nodes. Nodular target lesions may be recorded separately in design of the Case Report Form, or the collection method of other data. To judge whether there is complete response, it must meet that the short axis value of each node is < 10 mm. For PR, SD, and PD, the sum of the diameter of target lesions will include the measurement of the short axis of nodes.

Immeasurable target lesions due to too small size:

For all lesions (nodular and non-nodular lesions) recorded at baseline during the study, their measurements must be recorded in subsequent evaluations, despite too small (such as 2 mm).

However, the signals in CT scanning are sometimes too weak when lesions or lymph nodes are recorded at the critical value, and a radiologist may be possibly unwilling to give an accurate measurement, and reported as "too small to be measured".

In such case, it is very important to record the next measurement in the Case Report Form. If a radiologist considers that the lesion may disappear possibly, the measurement may be recorded as 0 mm. If the lesion is present definitely but the signal is too weak, it may be recorded as the default value 5 mm (this rule is not suitable for lymph nodes, as normal lymph nodes are in a definite size value and are often enwrapped by fatty tissues, such as retroperitoneal lymph nodes. However, if the lymph nodes are present definitely but the

signal is too weak and is difficult to measure, they may also be recorded as the default value 5 mm).

The default value 5 mm is originated from the thickness of CT scanning layers (if the thickness is changed, the default value shall not be changed). The measurements of such lesions (too small to be measured) may have no repeatability, and so a default value may prevent any mistaken measurement from which it is evaluated as false cure or false exacerbation. It is emphasized again that if a radiologist may provide an actual measurement, it shall also be recorded as 5 mm, even less than 5 mm.

Ruptured or fused lesions during treatment

According to the notes in Appendix II, when a non-nodular lesion is "ruptured", the sum of the diameter of the target lesions must be calculated by adding up the maximum diameter of all fragments. Similarly, when the lesions are fused, the maximum diameter between them may be kept; in this way, it may help obtain the maximum diameter value of each lesion prior to combination. If the lesions are fused completely and are no longer separated, the maximum diameter vector is the maximum diameter of the fused lesion.

4.3.3 Evaluation of Non-target Lesions

In this Section, the criteria for response of non-target lesions are defined. Although some non-target lesions are measurable actually, it is not necessary to measure them, and it is OK to carry out a qualitative evaluation at the timepoints specified by the protocol.

Complete response (CR): All non-target lesions disappear, and tumor markers are recovered to normal. All lymph nodes are of non-pathological size (the short diameter is <10 mm).

Incomplete response/non-progression of disease (non-CR or non PD): There is one or more non-target lesions and/or the level of tumor markers exceeds persistently the normal level.

Progression of disease (PD): A clear progression occurs in pre-existing non-target lesions. Notes: Occurrence of one or more new lesions may also be regarded as progression of disease.

4.3.4 Special Precautions for Evaluation of Non-target Lesion Progression

The definition of non-target lesion progression is explained additionally as follows: When a patient has measurable non-target lesions, even the target lesions are evaluated as stable disease or partial response, a definition of clear progression made on the basis of non-target lesions must meet the criteria that the whole exacerbation degree of non-target lesions has reached a level that the treatment must be terminated. However, a commonly increased size of one or more non-target lesions cannot reach frequently the criteria for progression; therefore, if the target lesions are stable or are of partial response, it is very rare that the whole tumor progression is defined on the single basis of any change of non-target lesions.

When a patient's non-target lesions are immeasurable: In some Phase III trials, when it is not specified that a measurable lesion is mandatory in the inclusion criteria, such case may occur. The whole evaluation is still carried out with reference to the above criteria; however, as there is no measurable data in such case, it is difficult to evaluate exacerbation of non-target lesions (according to the definition, it is mandatory that all non-target lesions are really immeasurable); therefore, when the change of non-target lesions results in increase of whole disease burden to a level equivalent to occurrence of progression of disease of the target lesions, it is required to establish an effective test method for evaluation, if the definition of clear progression is made, based on non-target lesions. For example, it is described as increased tumor burden equivalent to additional increase by 73% of the volume (equivalent to increase by 20% of the diameter of measurable lesions). For another example, peritoneal exudate is changed from "minor" to "massive", lymphatic disorder is changed from local to "extensively diffusive", or it is described as "sufficient to change the therapeutic method" in the protocol. The examples include: Peritoneal exudate changing from trace to massive, lymph involvement changing from primary site to distant diffusion, or "it is necessary to change the therapeutic regimen" as described in the protocol. If a clear progression is found, the patient is regarded as progression of disease at the timepoint as a whole. It is better to have an evaluation that the objective criteria is suitable for immeasurable lesions. Note: The newly added criteria must be reliable.

4.3.5 New Lesions

Occurrence of new malignant lesions heralds progression of disease; therefore, some evaluation aiming at the new change is very important. Presently, there are no specific criteria for radiological measurement of lesions. Nevertheless, the finding of a new lesion must be clear. For example, progression cannot be attributed to different radiological techniques, change of imaging morphology, or other lesions except tumor (such as some so-called new bone lesions are just healing of original lesions, or relapse of the original lesions). When the baseline lesions develop partial or complete response, this is very important; for example, some hepatic lesion necrosis may be defined as new cystic lesions in the CT report, and are not actually true.

Any lesion detected during follow-up but not detected at baseline is regarded as a new lesion, and suggests progression of disease. For example, a patient is found with visceral lesions at baseline examination, and is found with metastatic lesions at CT or MRI cranial examinations; thus the cranial metastatic lesion of the patient is regarded as evidence for progression of disease, even though he/she does not receive any cranial examination at baseline.

If a new lesion is unclear, for example, due to its small morphology, then a further treatment and follow-up evaluation is required to confirm whether it is a new lesion. If a reexamination confirms that it is really a new lesion, then the time to progression of disease shall be counted from the time when it is found initially.

An FDG-PET evaluation of lesions generally requires additional examinations for supplementary confirmation; the combination of FDG-PET examination and supplementary CT examination results for evaluation of progression (especially new suspected disease) is rational. If a new lesion may be confirmed by FDG-PET, it is carried out in accordance with the following procedure:

The results of FDG-PET examination at baseline are negative, and the results of subsequent FDG-PET examination during follow-up are positive, suggesting progression of disease;

No FDG-PET examination at baseline is conducted, and the results of subsequent FDG-PET examinations are positive;

If a new lesion found by the positive results of FDG-PET examination are consistent with the results of CT, then it is confirmed as progression of disease.

If a new lesion found by the positive results of FDG-PET examination is not confirmed by CT, then another CT has to be conducted (if it is confirmed, then the time to progression of disease is counted from the time when the abnormality is found by the previous FDG-PET examination).

If the positive results of FDG-PET examination are consistent with an existing lesion as indicated by CT, and the lesion is not progressive in radiological examination, then the disease is not progressive.

4.4 Optimal Overall Response Evaluation

Optimal overall response evaluation is the optimal response records from start of the trial to end of the trial, and meanwhile any essential conditions are considered for confirmation. Sometimes response effect occurs at the end of treatment; therefore in the protocol, it shall be clearly specified whether the response evaluation at the end of treatment is considered in the optimal overall response evaluation. In the protocol, it must be clearly specified how the new treatment affect optimal response effects prior to any progression. A patient's optimal response effects are mainly dependent on the results of target lesions and non-target lesions, as well as manifestations of new lesions. Moreover, they are also dependent on trial nature, protocol requirements, and measurement criteria of the results. Specifically speaking, in non-randomized trials, response effect are the primary goal, and PR or CR response confirmation is required, to confirm which is the optimal overall response effect.

4.4.1 Timepoint Response

Suppose that response effects may occur at specific timepoints in each protocol. The summary of overall response effects at each timepoint in the patient population with measurable disease at baseline is provided in Table 1.

See Table 2 for the evaluation, if the patients have no measurable lesions (without target lesions).

4.4.2 Explanation for missing evaluation or unevaluability

If lesion imaging or measurement cannot be conducted at a specific timepoint, then the patient is not evaluable at the timepoint. If only some lesions may be evaluated in an evaluation, generally such case is regarded as not evaluable at that timepoint, unless there is evidence that missing lesions do not impact the response effect evaluation at the specified timepoints. Such case may occur during progression of disease. For example: One patient may have 3 lesions with a sum of 50 mm at baseline; however, only 2 lesions are evaluable later, with a sum of 80 mm. Then the patient will be evaluated as with progression of disease, no matter how much impact the missing lesion has.

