8.1 Primary and secondary research variables

Primary variables:

Overall incidence of adverse events

Incidence of Grade 3/4 adverse events

Incidence of serious adverse events

Incidence of adverse events leading to permanent discontinuation

Incidence of adverse events leading to interruption/reduced dose

16-week progression-free survival rate

Secondary variable:

Effectiveness:

"Event occurrence date" variable: Calculated since the day when the informed consent is signed. If no event is observed, there is no date of end, and a so called cutoff observation has to be considered for analysis. The cutoff date is: The last date, such as for "last tumor measurement", "last medication registration", or "last visit".

Secondary efficacy variables include objective response rate, disease control rate, duration of response, progression-free survival, and overall survival.

Objective response rate (ORR): defined as the incidence of confirmed complete response (CR) or partial response (PR), the target lesions and non-target lesions are evaluated with validated radiological method and judged in accordance with RECIST criteria 1.1.

Progression-free survival (PFS): defined as the time from the signature of informed consent form to the first recording of progression of disease (PD) or date of death, whichever comes first. If no PD is observed, the censoring date should be the date of the last tumor measurement.

Overall survival (OS): defined as the time from the signature of informed consent form to date of death for any reason. If no death is observed, the last follow-up date is regarded as the censoring date.

Disease control rate (DCR): defined as the incidence of confirmed complete response (CR), partial response (PR) and stable disease (SD), the target lesions and non-target lesions are

evaluated with validated radiological method and judged in accordance with RECIST criteria 1.1.

Duration of response: defined as the time from the first recording of CR or PR to the first finding of PD for patients who have achieved response. For those with no record of PD after CR or PR, the censoring date is the date of the last tumor measurement.

Safety and Tolerability:

Safety and tolerability of the treatment are evaluated by incidence and severity of adverse events, laboratory tests, vital signs, ECG, LVEF, and ECOG performance status.

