In some cases, it is difficult to differentiate local lesions from normal tissues. If the evaluation of complete response is based on this definition, we recommend to carry out a biopsy prior to response evaluation of complete response of local lesions. When the abnormalities in the radiological examination results in some subjects are regarded as representing lesion fibrosis or scar formation, FDG-PET is taken as a similar evaluation standard to biopsy, and is used to confirm response of complete response. In such case, FDG-PET use shall be described prospectively in the protocol, and meanwhile the reports from specialized medical literatures aiming at such case are used as supportive evidence. However, it must be realized that, it will result in false positive results of complete response evaluation, due to restrictions of FDG-PET and biopsy (including extent of resolution and sensitivity for both of them).

Table 1 Timepoint Response: Subjects with Target Lesions (including non-target lesions or not)

Target Lesion	Non-Target lesions	New Lesions	Overall Response
CR	CR	No	CR
CR	Non CR/Non PD		PR
CR	Not evaluable		PR
PR	Non-progressive or not completely evaluable	No	PR
SD	Non-progressive or not completely evaluable	No	SD
Not completely evaluable	Non-progressive	No	NE
PD	Any situation	Yes or No	PD
Any situation	PD	Yes or No	PD
Any situation	Any situation	Yes	PD

CR = complete response	PR = partial response	SDStable disease	PD = progression of disease NE = not evaluable
------------------------	-----------------------	------------------	---

In SD patients, at least one follow-up measurement after enrolment must meet the SD criteria, and follow-up and enrolment are separated by at least 6-8 weeks.

Table 2 Timepoint Response - Subjects with only Non-target Lesions

Non-Target lesions	New Lesions	Overall Response
CR	No	CR
Non CR or non PD	No	Non CR/Non PD
Not completely evaluable	No	Not evaluable
Unclear PD	Yes or No	PD
Any situation	Yes	PD

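### Section 8.1 censors PFS and duration of response at the last tumor measurement, even when Appendix 2 makes that scan not evaluable

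*Protocol*

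**What the plan says.** Protocol section 8.1 starts the PFS clock at signature of the consent form and gives an explicit censoring rule: "If no PD is observed, the censoring date should be the date of the last tumor measurement". For duration of response the rule is the same: "the censoring date is the date of the last tumor measurement". A more general sentence in 8.1 on time-to-event variables offers the last tumor measurement, medication record or visit as examples of a cutoff date. None of these rules refers to whether the assessment was evaluable.

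Appendix 2 defines evaluability. Section 4.4.2 covers a visit without imaging: "If lesion imaging or measurement cannot be conducted at a specific timepoint, then the patient is not evaluable at the timepoint". For a visit that was only partly evaluated it says: "If only some lesions may be evaluated in an evaluation, generally such case is regarded as not evaluable at that timepoint". It then adds an exception: "unless there is evidence that missing lesions do not impact the response effect evaluation at the specified timepoints". Table 1 of Appendix 2 gives NE when the target lesions are "not completely evaluable", the non-target lesions have not progressed and there is no new lesion.

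Tumor assessment is every two cycles, that is every 8 weeks (section 6.2.1.2 and note 1 to the study flowchart). PFS at Week 16 is the primary efficacy endpoint of the expansion part (section 6.2.1.1), which plans about 20 patients (section 8.3).

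**The concern.** A censoring date should be the last time at which the patient was shown to be free of progression. Section 8.1 uses the last time at which a tumor was measured. The two differ when some target lesions were measured and others were not. That scan yields a measurement, but the sum of target diameters cannot be formed, so progression through growth of an unmeasured target lesion has not been excluded. Followed literally, the rule still keeps the patient at risk and progression-free up to that scan.

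The error has one direction. Later censoring enlarges the risk sets at event times up to the new date and removes no event, so every Kaplan-Meier estimate stays the same or rises. The expansion part has no concurrent control against which such a lift could cancel.

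**Working it through.** **Step 1: which visits are affected.**

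| Visit without PD | Appendix 2 result | Measurement present? | Sets the 8.1 censoring date? |
|---|---|---|---|
| No imaging or measurement | NE (4.4.2) | No | No |
| Some target lesions measured, non-target lesions not progressive, no new lesion | NE (Table 1; generally NE under 4.4.2) | Yes | Yes, as worded |
| All target lesions measured (PR or SD), non-target lesions incompletely evaluated, no new lesion | PR or SD (Table 1) | Yes | Yes, and properly so under Table 1 |

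Only the second row is a problem.

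**Step 2: the worked example in 4.4.2.** Three lesions total 50 mm at baseline. Later, two of them total 80 mm. The rise is (80 − 50)/50 = 60%, or 30 mm. That meets the progression rule of Appendix 2, 4.3.1 (20% and at least 5 mm) even if the missing lesion is counted as 0 mm. The example therefore illustrates the exception and is sound.

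**Step 3: possible size.** The protocol states no figure to reproduce and no rate of NE scans, so all counts here are assumptions. Take n = 20, e1 progressions at the first scan, e2 at the second, and k patients whose last scan is the second one and is NE.

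- As written: S = [(n − e1)/n] × [1 − e2/(n − e1)]
- Censored at the last evaluable scan: S = [(n − e1)/n] × [1 − e2/(n − e1 − k)]
- Lower bound, if all k had progressed: (n − e1 − e2 − k)/n

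The choice e1 = 6, e2 = 4 is scaled to the interim median of 3.7 months in section 3.1.2. That is 16.1 weeks, and an exponential curve gives 0.71 at 8 weeks and 0.50 at 16 weeks. As written, S = 0.70 × (1 − 4/14) = 50.0%.

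| k | Censored at last evaluable scan | If all k had progressed |
|---|---|---|
| 1 | 0.70 × (1 − 4/13) = 48.5% | 45% |
| 2 | 0.70 × (1 − 4/12) = 46.7% | 40% |
| 3 | 0.70 × (1 − 4/11) = 44.5% | 35% |
| 4 | 0.70 × (1 − 4/10) = 42.0% | 30% |

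With e1 = 4, e2 = 3 (65% as written) the shift is 1.0 to 5.0 points for k = 1 to 4. With e1 = 7, e2 = 5 (40% as written) it is 2.1 to 11.1 points. With k = 0 it is zero.

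**Step 4: where this falls on the PFS clock.** The second scan is due after four 28-day cycles, 4 × 28 = 112 days = 16 weeks after first dose. PFS starts at consent, which must precede screening procedures (6.1), and the flowchart places screening from Day −14. The second scan is therefore usually later than Week 16 on the PFS clock, by up to about two weeks. In the example, the four second-scan progressions and the NE scans then all lie beyond the landmark. With no event between the scans, the Kaplan-Meier value at 16 weeks is 14/20 = 70% under either rule.

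A partly measured first scan can still move the 16-week value. If k patients have only that scan and it is NE, the value as written is 1 − 6/20 = 70.0%. Censoring them at time zero gives 1 − 6/19 = 68.4%, 1 − 6/18 = 66.7% or 1 − 6/17 = 64.7% for k = 1, 2 or 3.

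**The case against.** The strongest reply is that what counts as a valid assessment for censoring is commonly settled in the statistical analysis plan, which is not at hand, and that 8.1 does not say a partial measurement counts as the last tumor measurement. The first half is fair as a matter of practice. But the protocol has itself fixed the date, in words that a partly measured scan satisfies. A plan that required evaluability would be tightening the protocol's definition.

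A second reply is that an NE scan is not empty. The Table 1 row requires no new lesion and no non-target progression, and evident growth on the measured target lesions would already be PD, as the 4.4.2 example shows. This stands, and it means such a patient cannot be described as wholly unobserved since the previous scan. The target sum is still missing, however, and Appendix 2 itself declines to call the visit stable.

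A third reply concerns the landmark: the second scan usually falls after Week 16 on the consent clock. This also stands, and it removes most of the effect that scan would have on the 16-week Kaplan-Meier figure.

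A reader might infer that Appendix 2 contradicts itself on partly evaluated visits. The documents do not support that. For target lesions the text and Table 1 agree on NE. They differ only where target lesions are PR or SD and non-target lesions are "Non-progressive or not completely evaluable", and then only if the 4.4.2 sentence is taken to cover non-target lesions. That sentence states a general default with an exception, and its example uses sums of diameters, which points to target lesions. The appendix also describes itself as an internal translation and refers to the English text.

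A reader might also infer that confirmed responses will be lost, since Table 3 turns PR followed by NE into SD or NE. But Appendix 2, 4.4.4 says that PR-NE-PR may be accepted as confirmation and leaves missing evaluations to the analysis plan. Nothing can be concluded on that from the protocol alone.

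**Conclusion.** The point holds in a narrow form and is minor. As worded, 8.1 lets a partly measured scan that Appendix 2 calls NE set the censoring date for PFS and duration of response. The patient is then carried as progression-free up to one 8-week interval too far when only the last scan is affected. The estimates can be lengthened or left unchanged, never shortened.

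It does not extend to every NE visit, because one without imaging has no measurement to date. The size cannot be established from the document. The shifts shown (1.5 to 8.0 points in the main example, 1.0 to 11.1 across those tried) rest on assumed event and NE counts and describe the curve after the second scan. A reader might take them as the bias in the 16-week endpoint, but the consent-based clock does not support that for the second scan. What remains exposed is the rest of the PFS curve, the median, duration of response and, through a partly measured first scan, the 16-week figure.

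**What to change.** In section 8.1, censor both PFS and duration of response at the last evaluable (not NE) tumor assessment without progression. Say also where a patient with no evaluable post-baseline assessment is censored, for example at the start of the PFS clock.

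As an optional clarification, note in Appendix 2, 4.4.2 that the partial-evaluation sentence refers to target lesions and that Table 1 governs incompletely evaluated non-target lesions.

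The change alters wording only. It uses data already collected and adds no visit or procedure. The one cost is that PFS and duration of response may come out slightly less favourable.
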